10.6.2 Secondary Endpoints

The secondary efficacy endpoints are the parameters described in Section 8.1.2 and safety variables in Section 8.2.

Recoveries

Results will be tested for the normality of distribution using the Shapiro-Wilk test and if normality is confirmed, an ANOVA will be performed for the recovery comparison (See Section 8.1.2.1 and 8.1.2.2).

Descriptive statistics will be presented on the number of recoveries at each timepoint and for each subject. These will be presented for each visit and for each subject and then for each batch of FVIII/ Optivate[®] used (see Section 8.1.2.1 and 8.1.2.2). Overall descriptive statistics will also be present for all subjects and all batches.

Bleeds

Bleed data will be summarised using summary statistics on two different bases: with each bleed as the experimental unit, and also with each subject as the experimental unit. Severity, duration of bleed, location and cause of bleed will be summarised separately, as well as being summarised in total. The treatment of new bleeds and ongoing bleeds will be listed. Also see Section 8.1.2.3.

Clinician's and subject's judgement of break-through bleed of treatment outcome

The data for clinician's and subject's assessment of bleeds will tabulated on separate tables, including the count for the number of bleeds not assessed. The tables will display the number and percentage of bleeds assessed for each category (*eg* very helpful, helpful etc.). This will be presented: Using all bleeds as the denominator and also the number of bleeds assessed as the denominator, displaying the number of bleeds not assessed.

Optivate[®] consumption

Dosing data will be summarised by treatment type *ie* prophylactic, preventative, to treat a bleed and overall. Total consumption data will be summarised using summary statistics on a per infusion and a per subject basis. Overall consumption data will be listed for each subject and summary statistics will also be displayed per month and year on a per subject basis (also see Section 8.1.2.4). Where a subject has completed less than a year of Optivate[®] treatment, the data will be extrapolated to calculate the per year consumption.

Exposure days

An exposure day is defined as a day in which the subject has received at least one dose of Optivate[®] (irrespective of treatment). The number of EDs will be listed for each subject. Descriptive statistics will be presented on a per month, per year and overall basis (also see Section 8.1.2.4).

NOTE: If antifibrinolytic agents have been administered during surgery, the surgery exposure days will not be included in the Optivate[®] ED calculations. Where a subject has completed less than a year of Optivate[®] treatment, the ED data will be extrapolated to calculate per year value.

Surgical Procedures

Descriptive narratives will be written for each surgical procedure and appended to the Clinical Study Report.

10.7 Safety Variables

The general strategy of the safety evaluation will be to examine the summaries for any trends. No formal hypothesis testing will be carried out.

10.7.1 Adverse Events

Adverse events (AEs) will be coded by the MedDRA (Medical Dictionary for Regulatory Authorities) system organ class and preferred term. Only treatment emergent AEs (*ie* beginning after dosing with Optivate[®]) will be included in the summary tables. All AEs (CRF and study diary) will be included in the data listings.

A bleed will not be reported as an adverse event, unless it represents a consistent worsening of FVIII deficiency symptoms or the subject is hospitalised. Bleed details will be recorded in the study diary by the subject. However, any excessive bleeding as a result of the surgery will be recorded as an adverse event.

Any complications of surgery that meet the definitions of a Serious Adverse Event (see Appendix I) will be reported as a Serious Adverse Events.

Adverse Drug Reactions (ADRs) will be defined as AEs which are recorded as having a possible, probable or very likely/certain causality related to Optivate[®]. If the Investigator cannot assign severity or causality as described in Appendix I, BPL will class the event as related. AEs leading to withdrawal will be defined as events where the Optivate[®] was discontinued as a result of the AE.

The denominator used for the calculation of percentages will be the number of subjects in the safety population. For all AE summaries described below, counting will be performed by subjects and event. For counts by subject, subjects experiencing the same event more than once will have that event counted only once within each system organ class and once within each preferred term.

The following summaries of treatment-emergent AEs will be provided:

Summary of AEs

All the AE data (from CRF and study diary) will be pooled together and reported in terms of the type, duration, treatment and/or severity.

The number and percentage of subjects reporting AEs, serious AEs (SAEs), ADRs, AEs leading to withdrawal and AEs leading to death. The number of AEs, SAEs, ADRs, AEs leading to withdrawal and SAEs leading to death.

Summary of AEs by Severity of Event

The number and percentage of subjects reporting AEs and ADRs, will be summarised by system organ class and by preferred term. The severity of event will be recorded once per subject for each preferred term as the maximum severity experienced by each subject (*ie* where the order of most severe to least severe is given by: severe, moderate then mild).

Summary of AEs by Causality

The number and percentage of subjects reporting AEs will be summarised by system organ class and by preferred term. The causality will be recorded once per subject for each term giving the most likely relationship to Optivate[®] (*ie* in the order: very likely/certain, probable, possible, unlikely, and unrelated).

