- Number of break-through bleeds including severity, duration, location and cause.
- Clinician's judgement of break-through bleed treatment outcome (excellent, good, moderate, poor).
- Subject's judgement of break-through bleed treatment outcome (very helpful, helpful, helped a little, did not help).
- Number of exposure days for each subject and per month/subject, per year/subject and overall.
- Total dose in IU/kg of Optivate[®] and average dose per infusion for prophylactic use, to treat a bleed, any additional preventative use and overall use; all analysed on a per subject basis.
- Total number of infusions for prophylactic use, to treat a bleed, any additional preventative use and overall use; all analysed on a per subject basis.
- Mean dose in IU/kg of Optivate[®] per subject/month and per subject/year for prophylactic use, to treat a bleed, any additional preventative use and overall use; all analysed on a per subject basis.
- Mean number of infusions per subject/month and per subject/year for prophylactic use, to treat a bleed, any additional preventative use and overall use; all analysed on a per subject basis.

[figure not shown]
PRIMARY EFFICACY ENDPOINT:

SECONDARY EFFICACY ENDPOINTS:

SAFETY ENDPOINTS: Viral serology, FVIII inhibitor (assessed as a primary efficacy endpoint), physical/medical examinations. Archive samples (1 mL serum) will be collected before first dose of Optivate[®] (V1) and at the End-of-Study Visit (V4). Also the number of AEs and Serious Adverse Drug Reactions as defined by ICH. The following medical events will automatically be considered as serious.

- Anaphylaxis or anaphylactoid reaction
- Myocardial infarction
- Stroke
- Pulmonary embolism
- Infection with any blood borne virus
- Any transmissible spongiform encephalopathy
- Development of inhibitors to Optivate[®]

Figure 1 Study visit flowchart

*recovery assessments will only be conducted after a 3 day wash-out period and if the subject is not actively bleeding ED= exposure days

[§] 28 days after the last infusion of Optivate[®] a safety Follow-Up will be conducted via telephone.

This study will be conducted in compliance with the protocol Europeon Union (EU) Clinical Trial Directives 2001/20/EC and 2005/28/EC and applicable local regulatory guidelines.

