5.3. SAFETY ENDPOINTS

The safety endpoints are:

- Viral serology.
- FVIII inhibitor (assessed as a primary efficacy endpoint).
- Physical/medical examinations.
- The number of AEs and Serious Adverse Drug Reactions as defined by ICH.
 Adverse drug reactions are defined as AEs which are recorded as having a
 possible, probable or very likely/certain causality related to Optivate[®]. The
 following medical events will automatically be considered as serious.
 - Anaphylaxis or anaphylactoid reaction
 - o Myocardial infarction
 - Stroke
 - o Pulmonary embolism
 - Infection with any blood borne virus
 - o Any transmissible spongiform encephalopathy
 - Development of inhibitors to Optivate[®]

Sponsor: BPL

Protocol: 8VWF07

Version: 1.0

Statistical Analysis Plan

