10.2. ADVERSE EVENTS

Adverse events will be coded to system organ classes and preferred terms using MedDRA version 16.1.

Treatment emergent AEs are defined as events that have onset following the first infusions of Optivate®, or events present before the first infusion of Optivate®, but which worsen in severity following the first infusion of Optivate®. Should the time of onset be missing, but the date of onset be equal to the date of first dosing with Optivate®, then it will be assumed such events are treatment emergent.

Should the day of onset be missing, for the purposes of assigning treatment emergence, the day will be taken to be 01, unless the month and year are the same as the month and year of first infusion of Optivate[®], in which case the date of first infusion of Optivate[®] will be taken.

Should the day and month be missing, for the purposes of assigning treatment emergence, the day and month will be taken to be 01 January, unless the year is the same as the year of first infusion of Optivate®, in which case the date of first infusion of Optivate® will be taken.

All adverse events will be listed, however only treatment emergent adverse events will be included in the summary tables.

Sponsor: BPL

Protocol: 8VWF07

Version: 1.0

Statistical Analysis Plan

Where severity or causality is missing for an event, for the purposes of the tables, these will be assumed to be severe and very likely/certain respectively. Similarly, where severity or causality changes during the course of the event, the worst case will be taken for the analysis.

Summary tables presenting frequency of AEs by SOC and PT will be ordered by overall descending frequency of SOC and then, within a SOC, by overall descending frequency of PT.

The following tables of adverse events will be produced:

- An overall summary of the number and percentage of subjects reporting TEAEs, serious TEAEs, treatment related TEAEs, TEAEs leading to withdrawal and TEAEs leading to death
- TEAEs overall and by system organ class and preferred term
- Study treatment related TEAEs overall and by system organ class and preferred term. Study-treatment related events are those recorded as having a possible, probable, or very likely/certain causality related to Optivate®.
- TEAEs by maximum severity, overall and by system organ class and preferred term
- Serious TEAEs, overall and by system organ class and preferred term

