- Study treatment related serious TEAEs overall and by system organ class and preferred term. Study-treatment related events are those recorded as having a possible, probable, or very likely/certain causality related to Optivate[®].
- TEAEs by maximum relationship to study treatment, overall and by system organ class and preferred term
- TEAEs leading to drug withdrawal, overall and by system organ class and preferred term

Where a subject has multiple events within a given system organ class or preferred term, the subject will only be counted once within that system organ class or preferred term.

For summaries by severity or relationship to study treatment, where a subject has multiple events within a given system organ class or preferred term, the subject will

Sponsor: BPL

Protocol: 8VWF07

Version: 1.0

Statistical Analysis Plan

only be counted once at the maximum severity/worst case relationship at which an event occurred within that system organ class or preferred term.

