12. CHANGE FROM ANALYSIS PLANNED IN PROTOCOL

There are no changes to the analyses planned in the protocol.

Sponsor: BPL

Protocol: 8VWF07

Version: 1.0

Statistical Analysis Plan

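### The protocol and the SAP's own safety endpoint call for numbers of adverse events, but the SAP's adverse event section and table index specify counts of subjects only, and the SAP declares no change from the protocol.

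*Protocol*

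**What the plan says.** **Protocol.** Section 10.7.1 sets a general rule: "For all AE summaries described below, counting will be performed by subjects and event". The rule that a subject is counted once within a system organ class (SOC) or preferred term (PT) is limited there to counts by subject. For the overall summary the section asks first for numbers and percentages of subjects, then separately for event totals: "The number of AEs, SAEs, ADRs, AEs leading to withdrawal and SAEs leading to death". The synopsis lists among the safety endpoints: "Also the number of AEs and Serious Adverse Drug Reactions as defined by ICH".

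**SAP.** Section 5.3 carries the same endpoint forward: "The number of AEs and Serious Adverse Drug Reactions as defined by ICH". Section 10.2 then defines the overall table as "An overall summary of the number and percentage of subjects reporting TEAEs, serious TEAEs, treatment related TEAEs, TEAEs leading to withdrawal", with deaths as the last item. Its rule for repeated events is that "the subject will only be counted once within that system organ class or preferred term", and the severity and relationship tables count a subject once at the worst case. The index lists eight AE tables, 14.3.1.1 to 14.3.1.8, and all but the first are titled as numbers and percentages of subjects. Section 12 states: "There are no changes to the analyses planned in the protocol".

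**The concern.** The number of adverse events and the number of subjects with an adverse event are different quantities, and Protocol 10.7.1 asks for both. A statistician who follows SAP 10.2 and the index would produce only the second. The endpoint in SAP 5.3 would then have no table, and because SAP 12 declares no departure, a reader of the study report would not know that a planned output had been dropped.

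This is a post-marketing safety study in which Protocol 10.7 relies on looking through the summaries for trends. With 10 to 12 subjects, one subject is 1/12 = 8.3 to 1/10 = 10 percentage points. A subject with one reaction and a subject with several of the same kind add the same amount to a subject-count table. Event totals are what separate the two cases in the summaries.

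**Working it through.** The point is one of consistency between texts. Neither document gives a figure to reproduce, so the check sets the passages side by side and tallies the unit of counting.

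**Step 1. Event totals named in Protocol 10.7.1 against the overall summary in SAP 10.2.**

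| Protocol event total | Nearest item in SAP 10.2 | Unit in SAP |
|---|---|---|
| AEs | TEAEs | subjects |
| SAEs | serious TEAEs | subjects |
| ADRs | treatment-related TEAEs | subjects |
| AEs leading to withdrawal | TEAEs leading to withdrawal | subjects |
| SAEs leading to death | TEAEs leading to death | subjects |

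All 5 have a subject-count counterpart; 0 of 5 have an event count.

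**Step 2. The eight AE tables in the SAP index.**

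- Table 14.3.1.1 (overall summary): the title is neutral, but SAP 10.2 describes the content as subjects.
- Tables 14.3.1.2 to 14.3.1.5 and 14.3.1.8 (all, serious, related, related serious, leading to drug withdrawal): five tables by SOC and PT, titled by subject.
- Tables 14.3.1.6 and 14.3.1.7 (severity, relationship): two tables, titled by subject.

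That is 1 + 5 + 2 = 8 tables, all specified by subject and none with an event count.

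**Step 3. Which of the eight depart from the protocol.** The paragraphs of Protocol 10.7.1 on severity and causality ask for numbers and percentages of subjects, each recorded once at the worst grade or most likely relationship. The SAP matches this, so Tables 14.3.1.6 and 14.3.1.7 are not clear departures. The overall table departs from an explicit sentence. The five SOC/PT tables depart only from the general counting rule, since the protocol describes no such stand-alone tables. The discrepancy is therefore firm for 1 table, rests on the general rule for 5, and does not reach 2.

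**Step 4. Where events do appear.** SAP 10.2 lists all AEs, and Listings 32 to 34 cover AEs, SAEs and AEs leading to withdrawal of study drug. Totals could be counted from these by hand, after separating treatment-emergent events from the rest, because both documents restrict the summary tables to treatment-emergent events.

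**Step 5. A comparison within the SAP.** For break-through bleeds, SAP 9.2.3 asks for the number of subjects with bleeds and also the total number of bleeds. The two-unit layout is already in use elsewhere in the plan, and no reason is given for leaving it out of the AE section.

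**The case against.** Several counter-arguments have weight.

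- **The table shells are not available.** SAP 19.1 places them in an attachment, and Table 14.3.1.1 might contain an event column. This stands as a limit: one cannot say that the totals will never be tabulated, only that neither the SAP text nor the index calls for them.
- **The endpoint might be loose wording for incidence.** Taken alone, a number of AEs could mean subjects with AEs. Protocol 10.7.1 rules this out for the overall summary by asking for subject counts and event totals in separate sentences.
- **SAP 12 may have been true when written.** The SAP is version 1.0 and the supplied protocol is version 4. The SAP gives 56 weeks per subject where the protocol gives 60, so it may rest on an earlier protocol. The statement is inaccurate against the supplied version; whether it was wrong at the time is unknown.
- **Event counts add little for some rows.** This is fair for death and largely so for withdrawal, but not for AEs, SAEs or ADRs.

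A reader might infer more than the documents support:

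- *That every SAP table counts subjects only.* The bleed tables count events.
- *That repeated reactions in one subject become invisible.* Every AE is listed, and with 10 to 12 subjects repeats can be found there. The gap is in tabulation.
- *That subject percentages will saturate.* If events were independent at an assumed 2 per subject, 1 - exp(-2) = 86% would have at least one; at 4, 1 - exp(-4) = 98%. The documents give no expected AE rate, and the figures concern only the any-AE row. SOC and PT rows saturate less readily. Nothing here rests on them.
- *That the protocol requires AE rates per infusion or per patient-year.* It does not.

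**Conclusion.** The discrepancy holds for the overall AE summary: all five event totals named in Protocol 10.7.1, and the endpoint in SAP 5.3, are missing from the tables as the SAP describes them. Under the general counting rule it extends to the five SOC/PT tables. It does not extend to the severity and causality tables.

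The consequence is moderate. The primary endpoint, inhibitor development, is untouched, safety is descriptive without hypothesis tests, and the events are collected and listed. What is at stake is that a stated endpoint would be reported only through listings, under a declaration that nothing changed. The conclusion assumes that the unsupplied shells follow the SAP text, and that version 4 is the protocol against which SAP 12 should be judged.

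**What to change.** 1. In SAP 10.2 and Table 14.3.1.1, add the number of events beside the number and percentage of subjects for the five protocol totals, restricted to treatment-emergent events, and add the number of serious ADRs.
2. Add an event-count column to Tables 14.3.1.2 to 14.3.1.5 and 14.3.1.8. Leave Tables 14.3.1.6 and 14.3.1.7 once per subject.
3. State a rule for counting events. It should treat an event that changes severity or causality as one event at its worst case, as SAP 10.2 already implies. It should also check for duplicates when CRF and diary records are pooled, since a duplicate inflates an event count but not a subject count.
4. If event counts are deliberately omitted, say so in SAP 12 with the reason and align SAP 5.3. In either case, have SAP 12 name the protocol version it refers to.

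The cost is one column in six tables, one short rule and an edit to SAP 12. No new data are needed. Event rates per infusion or per patient-year are optional; the SAP already plans the denominators (time on study in 8.1, infusions in 9.2.5).

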10.7.2 Viral serology variables

Shift tables for virology will present the number of subjects with positive and negative serology results and those for whom the results change during the study.

10.7.3 Physical/Medical Examination

Physical/Medical examination details will be listed. Any adverse change will be reported as an adverse event, as described in Section 10.7.1.

10.8 Determination of Sample Size

No formal sample size calculation was performed, as no formal hypothesis testing is planned. The sample size of 10 evaluable subjects was agreed with the German regulatory authority as part of the licencing agreement for Optivate[®]. Therefore for this study 12 subjects will be enrolled to ensure data for 10 evaluable subjects.

11.

INVESTIGATOR'S STATEMENT

Multicentre, Non-controlled, Prospective, Post-Marketing Safety Study Following Long-Term Prophylactic Optivate[®] Treatment in Subjects with Severe Haemophilia A.

STUDY CODE: 8VWF07

FINAL PROTOCOL

Version 4, 30 November 2015

I have been adequately informed about the development of the IMP to date and agree that this study protocol contains all the information required to conduct the study.

I will provide copies of the study protocol and all product information relating to prior product experience furnished to me by the Sponsor/CRO to all staff responsible to me who participate in this study. I will discuss this material with them to ensure that they are fully informed regarding the product and the conduct of the study.

The information contained in this document is CONFIDENTIAL and, except to the extent necessary to obtain informed consent, may not be disclosed, unless such disclosure is required by government regulation or local customs or law. Persons to whom the information is disclosed must be informed that the information is CONFIDENTIAL and cannot be disclosed by them.

By my signature below I agree to conduct this clinical trial in accordance with the protocol, Good Clinical Practice (GCP), government regulations, and local customs or laws, including those applying to institutional/ethics review and informed consent.

I agree to ensure the confidentiality of the subjects enrolled under my care; however, I agree to make their medical records available to authorised representatives of the CRO; authorised representatives of Bio Products Laboratory Ltd., the sponsor of this clinical trial; and relevant regulatory authorities.

I have read the Summary of Product Characteristics for Optivate[®] and protocol, and I am aware of my responsibilities as a Principal Investigator.

Signature:		Date:
	Principal Investigator	
Name:		
	(Printed)	

APPENDIX I - ADVERSE EVENT DEFINITIONS AND REPORTING PROCEDURES

ABBREVIATIONS

- Adverse Drug Reaction	
- Adverse Event	
- Bio Products Laboratory Limited	
- Case Record Form	
- Electronic Case Record Form	
- Electrocardiogram	
- Informed Consent Form	
- Independent Ethics Committee	
- Institutional Review Board	
- Investigational Medicinal Product	
- Medicines and Healthcare Products Regulatory Agency	
- Serious Adverse Event	
- Summary of Product Characteristics	
- Suspected Unexpected Serious Adverse Reaction	

